**Table 6. Areas of Safety Interest (Continued)**

ASI Grouping	Categories (ASI)	Search Criteria	Terms to Display	Include in AE Overview (Y/N)
Hypersensitivity Reaction	Hypersensitivity	Narrow – Hypersensitivity (SMQ 20000214)	PTs	Y – serious events only
	Anaphylactic Reaction	Narrow – Anaphylactic reaction (SMQ 20000021)	PTs	N
Hepatic Events	Hepatic Events	Broad – Hepatic failure, fibrosis and cirrhosis and other liver damage-related conditions (SMQ 20000013)	PTs	N
		Broad – Hepatitis, non-infectious (SMQ 20000010)		
		Broad – Cholestasis and jaundice of hepatic origin (SMQ 20000009)		
		Broad – Liver related investigations, signs and symptoms (SMQ 20000008)		
		Narrow – Liver-related coagulation and bleeding disturbances (SMQ 20000015)		

## **Adverse Event per 100 Patient-Years of Exposure**

AEs occurring during the entire study will be presented by event rate per 100 patient-years. These will be presented for any TEAEs, serious adverse events, Areas of Safety Interest.

AEs per 100 patient-years of exposure is defined as the number of AEs divided by the total exposure in 100 patient-years. Note that one event per preferred term per day per subject will be counted in the calculation of the number of AEs (i.e., a preferred term will not be counted twice on the same day for the same subject). See the calculation method below.

$$100 \times \frac{\text{Number of TEAEs}}{\text{Total Patient Years}}$$

where total patient years is defined as the sum of the study drug exposure (defined as date of last dose – date of first dose + 105 days or + 7 / 49 (sensitivity analysis) days for risankizumab or FUMADERM®, respectively) of all subjects normalized by 365.25, and rounded to one decimal place.

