## **5.0 Investigational Plan**

### **5.1 Overall Study Design and Plan: Description**

This is a randomized, controlled, multicenter, open-label study with blinded assessment of efficacy to demonstrate the efficacy and safety of SC risankizumab in adult subjects with moderate to severe plaque psoriasis who are naïve to and candidates for systemic therapy as compared with oral FUMADERM® provided as study medication. Eligible male and female subjects with moderate to severe plaque psoriasis will be selected to participate in the study according to the selection criteria.

The study will include a 30-day screening period and a 24 week active-controlled treatment period followed by a follow-up phone call at Week 31 for subjects that do not elect to enroll into the extension study. The maximum study duration is approximately 35 weeks for subjects that do not elect to enroll into the extension study and approximately 28 weeks for subjects that do participate in the extension study. This study was designed to enroll 110 subjects to meet scientific and regulatory objectives without enrolling an undue number of subjects in alignment with ethical considerations. Therefore, if the target number of subjects has been enrolled, there is a possibility that additional subjects in screening will not be enrolled.

After meeting the selection criteria, enrolled subjects will be randomly assigned in a 1:1 ratio to one of two arms as shown below:

- Risankizumab 150 mg SC at Week 0/Day 1, Week 4 and Week 16 or,
- Oral FUMADERM® INITIAL provided as study medication starting at Week 0/Day 1 until Week 2 and FUMADERM® provided as study medication starting at Week 3 until Week 24 (last intake in the morning on the day of Week 24 visit):

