If, during the course of study drug administration, the subject prematurely discontinues study drug use, the procedures outlined for the Early Termination Visit must be completed within 2 weeks after the decision to discontinue, and preferably prior to the initiation of another therapy. However, these procedures should not interfere with the initiation of any new treatments or therapeutic modalities that the Investigator feels are necessary to treat the subject's condition. Following discontinuation of the study drug, the subject will be treated in accordance with the Investigator's best clinical judgment.

A final telephone call will occur for all subjects who do not roll over into the extension study, approximately 15 weeks after the last dose of risankizumab and 7 weeks after the last dose of FUMADERM®, provided as study medication, to determine the status of any ongoing AEs/SAEs or the occurrence of any new AEs/SAEs.

All attempts must be made to determine the date of the last study drug dose and the primary reason for early termination. The information will be recorded on the appropriate eCRF page.

For subjects that are considered lost to follow-up, reasonable attempts must be made to obtain information on the final status of the subject. At a minimum, two phone calls must be made and one certified letter must be sent and documented in the subject's source documentation.

Subjects who discontinue the study prematurely will not be replaced.

Subjects are considered study completers if they have completed the Week 24 visit.

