### **8.1.5 Analysis of Safety**

All safety analyses will be performed in the safety population.

Treatment-emergent adverse events are defined as events with an onset date on or after the first dose of study drug until 15 weeks (105 days) following the last dose of risankizumab or 1 week (7 days) after the last dose of FUMADERM® provided as study medication or until rollover into the extension study. In a sensitivity analysis, adverse events with an onset date until 7 weeks (49 days) after the last dose of FUMADERM® provided as study medication or until rollover into the extension study will be included.

SAEs and protocol-related non-serious AEs with onset after informed consent but before the first study drug administration will be considered as pretreatment events and reported separately.

Adverse events will be tabulated by system organ class and preferred term, whereby the most current implemented MedDRA dictionary will be used. Also, summaries by severity and relationship to study drug will be done. Certain adverse events, like serious or severe, leading to discontinuation, will be listed and described in detail. Adverse events of interest for treatment with biologics will be defined in the statistical analysis plan and analyzed separately.

Adverse events will be summarized by frequency and percentage and presented by treatment group, statistical comparisons will be performed using Fisher's exact test.

Other safety variables like laboratory data and vital signs will also be described by descriptive statistics for each treatment group. Treatment comparisons will be performed by one way ANOVA. In addition, shift tables and listings will be provided for abnormal values, whereby the normal range of the analyzing laboratory will be used.

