- b. Subjects that discontinue the study prior to the end of the study will have a follow-up phone call within 15 weeks after the last dose of FUMADERM® provided as study medication for collection of safety data. Subjects that elect to enroll into a separate extension study will not require the Week 31 Follow-Up phone call as part of this trial.
- c. Update history.
- d. Serum pregnancy test in all women at screening and if the urine pregnancy test is positive at any other visit. Urine pregnancy tests are to be performed in all women of child bearing potential prior to administration of study drug at all dosing visits.
- e. Height and weight will be measured at the Screening Visit only (with shoes off).
- f. Targeted laboratory samples should be limited to CBC with differential count (hematology), serum creatinine (substrates) and ALT, AST, gamma-GT and AP (enzymes).
- g. (FSH) To be done at Screening in all women aged ≤ 55 years with no menses for 12 or more months without an alternative medical cause.
- h. Infection screening consists of Hepatitis B Surface Antigen (qualitative), Hepatitis B Surface Antibody (qualitative), Total Hepatitis B Core Antibodies (qualitative), Hepatitis B Virus DNA (quantitative) reflex, Hepatitis C Virus RNA (quantitative) reflex, HIV-1 and HIV-2 Antibody (qualitative), PPD/QuantiFERON-TB.
- i. For FUMADERM® INITIAL and FUMADERM® provided as study medication only.
- j. Prior to other procedures.
- k. SC risankizumab 150 mg at Week 0/Day 1, Week 4 and Week 16. Risankizumab will be administered at the study site by authorized site personnel (e.g., study nurse) after all study procedures have been completed.
- l. Oral FUMADERM® daily starting at Week 0/Day 1 and until Week 24 (the last dose will be in the morning of the day of Week 24 visit). FUMADERM® INITIAL starting at Week 0/Day 1 until Week 2 and FUMADERM® starting at Week 3, both at starting dose of 1 tablet per day, followed by a dose increase of one tablet per week, depending on efficacy response and tolerability. The maximum dose of FUMADERM® of 6 tablets per day should not be exceeded.
- m. PK and ADA samples are collected only from the subjects receiving risankizumab.

---

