**11.0 Safety Analysis****11.1 General Considerations**

Safety evaluations include AE monitoring, physical examinations, vital sign measurements, and clinical laboratory testing (hematology, chemistry, and urinalysis) as a measure of safety and tolerability for the entire study duration. Safety summaries will be provided using the safety population as defined in Section 5.1. Pairwise comparisons of risankizumab vs FUMADERM® will be performed in the Safety Population. AEs will be analyzed using Fisher's exact test, only P values  $\leq 0.100$ , when rounded to three digits, will be presented.

Missing safety evaluations will not be imputed.

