## **11.2 Analysis of Adverse Events**

### **11.2.1 Treatment-Emergent Adverse Events**

Treatment-emergent adverse events (TEAE) are defined as events with an onset date on or after the first dose of study drug until 15 weeks (105 days) following the last dose of risankizumab or 1 week (7 days) after the last dose of FUMADERM® or until rollover into the extension study. In a sensitivity analysis, adverse events with an onset date until 7 weeks (49 days) after the last dose of FUMADERM® or until rollover into the extension study will be included. In this sensitivity analysis, the observation period for TEAEs will be identical for both treatment arms, i.e., up to the 31 week safety follow-up call.

SAEs and protocol-related non-serious AEs with onset after informed consent but before the first study drug administration will be considered as pretreatment events and reported separately. Posttreatment events for FUMADERM® are included in the above sensitivity analysis.

If an incomplete onset date is collected for an adverse event, the event will be assumed to be treatment-emergent unless there is other evidence that confirms that the event is not treatment-emergent (e.g., the event end date is prior to the study drug start date).

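### Adverse event rates per 100 patient-years stop counting events at rollover but credit person-time beyond it, which lowers the rates, and lowers them more for risankizumab

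*SAP*

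**What the plan says.** **Numerator.** The rate formula (SAP 11.2.1, Adverse Event per 100 Patient-Years of Exposure) counts TEAEs, so the TEAE definition earlier in 11.2.1 applies. The window runs to 105 days after the last risankizumab dose, "or 1 week (7 days) after the last dose of FUMADERM® or until rollover into the extension study". Protocol 8.1.5 has the same rule and repeats the rollover limit for the 49-day sensitivity window: "after the last dose of FUMADERM® provided as study medication or until rollover into the extension study".

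**Denominator.** Total patient-years sum, over subjects, "date of last dose – date of first dose + 105 days or + 7 / 49 (sensitivity analysis) days". Neither document limits this at rollover.

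**Follow-up after rollover.** Every Week 24 completer is offered the extension. Protocol Appendix C, footnote b, states: "Subjects that elect to enroll into a separate extension study will not require the Week 31 Follow-Up phone call as part of this trial". Protocol 5.1 gives a total study duration, screening included, of "approximately 28 weeks for subjects that do participate in the extension study". For everyone else, Protocol 5.4.1 plans a last contact: "A final telephone call will occur for all subjects who do not roll over into the extension study".

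**Sensitivity analysis.** SAP 11.2.1 says that with the 49-day tail "the observation period for TEAEs will be identical for both treatment arms, i.e., up to the 31 week safety follow-up call".

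**The concern.** A rate is interpretable only if events and person-time cover the same period. Here a subject who rolls over adds days to the denominator during which, by the SAP's own definition, no event can enter the numerator. The rate is therefore too low.

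The surplus differs by arm. Risankizumab is last given at Week 16 and carries a 105-day tail, which reaches Week 31. FUMADERM is taken until Week 24 and carries only a 7-day tail in the main analysis. The main rate table would thus lower the risankizumab rate much more than the FUMADERM rate. The tables concerned are those for any TEAE, serious adverse events and Areas of Safety Interest, which are the exposure-adjusted safety comparison of an open-label trial.

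**Working it through.** **Inputs**

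- Visit days (Protocol Appendix C): first dose Day 1, Week 16 Day 113, Week 24 Day 169, follow-up call Day 218.
- Last dose (Protocol 5.1): risankizumab at Week 16, FUMADERM on the morning of the Week 24 visit.
- Tails (SAP 11.2.1): 105 days for risankizumab; 7 days (main) or 49 days (sensitivity) for FUMADERM.
- Rollover date: taken as the Week 24 visit, when the extension is offered. This is an assumption.
- Rollover share among completers, r: not in the documents, so a range is shown.

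**The plan's own horizon.** 113 + 105 = 218, 169 + 49 = 218 and 31 × 7 + 1 = 218. The Week 31 call on Day 218 is reproduced.

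**Days per completer who rolls over**

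| Arm and analysis | Credited | Events counted | Surplus |
|---|---|---|---|
| Risankizumab | 112 + 105 = 217 | 168 | 49 (22.6%) |
| FUMADERM, main | 168 + 7 = 175 | 168 | 7 (4.0%) |
| FUMADERM, 49-day | 168 + 49 = 217 | 168 | 49 (22.6%) |

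**Effect on the rates, all subjects completing.** Planned rate ÷ correct rate = [(1 − r) × credited + r × 168] ÷ credited. For risankizumab this is (217 − 49r)/217 = 1 − 0.226r; for FUMADERM in the main analysis it is (175 − 7r)/175 = 1 − 0.04r.

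| r (same in both arms) | Risankizumab understated by | FUMADERM main understated by | Ratio shown when the true ratio is 1.00 |
|---|---|---|---|
| 0% | 0% | 0% | 1.00 |
| 50% | 11.3% | 2.0% | 0.887/0.980 = 0.91 |
| 90% | 20.3% | 3.6% | 0.797/0.964 = 0.83 |
| 100% | 22.6% | 4.0% | 0.774/0.960 = 0.81 |

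In the 49-day analysis both arms carry the risankizumab factor. The ratio stays at 1.00 and both rates are understated by 11.3%, 20.3% and 22.6% at r = 50%, 90% and 100%.

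**In patient-years, 55 completers who all roll over.** Events are counted over 55 × 168/365.25 = 25.3. Credited time is 55 × 217/365.25 = 32.7 for risankizumab (and for FUMADERM in the 49-day analysis) and 55 × 175/365.25 = 26.4 for FUMADERM in the main analysis.

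**When the arms are not balanced (assumed scenarios)**

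- Rollover 90% on risankizumab and 50% on FUMADERM, all completing: the 49-day ratio reads 0.797/0.887 = 0.90.
- All risankizumab subjects complete; 24% of FUMADERM subjects stop, which borrows the adverse event discontinuation figure from Protocol 3.0, with last dose 28 to 84 days after first dose; 90% of completers roll over; stoppers are fully followed. The ratio reads 0.82 to 0.83 in the main analysis and 0.96 to 0.98 in the 49-day analysis. For a last dose at 28 days, the main FUMADERM factor is (0.76 × 168.7 + 0.24 × 35)/(0.76 × 175 + 0.24 × 35) = 136.6/141.4 = 0.966, and 0.797/0.966 = 0.825.

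**Sensitivity to the nominal days.** The 4-day visit window moves the 22.6% between 41/213 = 19.2% (Week 16 late credit shortened, last dose Day 109, Week 24 on Day 173) and 57/221 = 25.8% (last dose Day 117, Week 24 on Day 165). If the risankizumab subjects who do not roll over stopped early with 105 or 133 days credited, and 90% of the arm rolls over, the understatement is 44.1/205.8 = 21.4% or 44.1/208.6 = 21.1%, instead of 20.3%.

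**The case against.** The best defence of the plan has five parts.

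- **The denominator may be meant as drug exposure, not time at risk.** This does not stand. SAP 9.0 defines risankizumab exposure separately, with 84 days added. The rate formula uses 105, 7 and 49 days, which are exactly the TEAE tails. It was built to match the TEAE window and lacks only the rollover limit.
- **Safety data are collected for 15 or 7 weeks after the last dose, with no exception for rollover** (Protocol 5.1 and 6.1.4). That is what those sections say, but an event after rollover is not a TEAE under SAP 11.2.1, so it cannot enter the numerator even if it is recorded.
- **The size is conditional.** This stands. The effect is confined to subjects who roll over and is zero if nobody does. A rollover date after the Week 24 visit removes surplus day for day. The statement that early terminators are unaffected rests on the final call in Protocol 5.4.1 taking place about 15 or 7 weeks after the last dose. Appendix C, footnote b, describes the timing of that call differently.
- **The sensitivity analysis already treats the arms alike.** This stands in part. The period ends at Week 24 for rollover subjects and at Week 31 for the others, in both arms. Only the statement that it runs to the Week 31 call is wrong for rollover subjects. The ratio is protected only if completion and rollover are balanced, and the absolute rates are not protected.
- **The rates are descriptive.** This also stands. The SAP gives no test or interval for them. It does say "Pairwise comparisons of risankizumab vs FUMADERM® will be performed in the Safety Population", but the test named there is Fisher's exact test on adverse events, which does not use person-time.

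**Conclusion.** The concern holds. Followed as written, the SAP divides events counted to rollover by person-time that runs past it. For a share r of completers rolling over at the Week 24 visit, on nominal visit days and with all subjects completing, the main analysis understates the risankizumab rate by r × 22.6% and the FUMADERM rate by r × 4.0%. A true rate ratio of 1.00 would then read between 1.00 (r = 0) and 0.81 (r = 100%). The actual r is unknown, but the direction is not: whenever r is above zero and similar in both arms, the main table favours risankizumab. In the 49-day table both rates are too low by r × 22.6%, and the ratio is correct only under balance.

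The primary endpoint, the subject-level incidence tables and the Fisher's exact tests do not change. This should be fixed before database lock, but it does not threaten the trial's main conclusion.

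**What to change.** Keep the rate formula and its day count, and end each subject's person-time when TEAE counting ends:

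person-time = min(last dose date + 105 / 7 / 49 days, rollover date, date of death, date of last study contact if the planned final call did not take place) − first dose date.

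Apply this in both the main and the 49-day rate tables, with the same rollover date as in the TEAE definition. A rollover completer then contributes 168 days in either arm, and mean risankizumab person-time per completer becomes 217 − 49r days. In SAP 11.2.1, limit the statement that observation runs to the Week 31 call to subjects who do not roll over.

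The SAP already uses a minimum rule of this kind: the footnotes to the visit-window tables in Section 6.0 cap safety windows at 105 or 7 days after the last dose. The cost is one sentence in the SAP and one line of code, using dosing, rollover, death and last-contact dates. The downside for the sponsor is that the reported risankizumab rates become less favourable.

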### **11.2.2 SAEs (Including Deaths) and Adverse Events Leading to Study Drug Discontinuation**

Deaths and all SAEs will be presented in listing format. In addition, SAEs will be summarized by System Organ Class and MedDRA Preferred Term.

### **11.2.3 Safety Subgroup Analysis**

The AE overview and AE by SOC and preferred term will also be analyzed by stratification factor prior phototherapy (yes, no) as well as gender (male, female), age (< 65 years; 65 – 74 years; ≥ 75 years) and weight (≤ 100 kg, > 100 kg).

## **11.3 Analysis of Laboratory Data**

For the assessments of laboratory data, values observed more than 105 days after the last dose of risankizumab and 7 days after the last dose of FUMADERM will be excluded (see Section 6.0, Definition of final observation).

Listing and descriptive statistics of laboratory values over time, change from baseline, and extreme abnormal value on treatment will be provided. Extreme abnormal value is the value which is most significantly away from the reference range. Frequency of subjects with transitions relative to reference range and listing of subjects with significant abnormal laboratory values will be presented as well.

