### **Treatment Period**

This period will begin at the Week 0/Day 1 (Baseline) Visit and will end at the Week 24/Early Termination (ET) Visit. At the Baseline Visit, subjects who meet all the inclusion criteria and none of the exclusion criteria described in Section [5.2](#) will be enrolled into the study and randomized to open-label treatment. During this period of the study, subjects will visit the site at Week 0 (Day 1/Baseline), Week 4, Week 8, Week 12, Week 16, Week 20 and Week 24/ET. A  $\pm$  4 day window is permitted around scheduled study visits. If any visit has to be rescheduled, subsequent visits should follow the original visit date schedule. Visits should take place on the same day of the week as much as possible. At the Week 24 visit, subjects who have completed the study will be offered the opportunity to participate in a separate extension study. For subjects that do not elect to enroll into the extension study, a follow-up phone call will be performed at Week 31.

Safety data will be collected throughout the treatment period and up to 15 weeks after the last dose of risankizumab and/or 7 weeks after the last dose of FUMADERM® provided as study medication in this study. Subjects may discontinue study drug treatment at any time during study participation. Subjects that discontinue the study prior to Week 24 will have an ET visit and complete the procedures outlined in [Appendix C](#) within 2 weeks

[figure not shown]
after the decision to discontinue and preferably prior to the administration of any new therapies.

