### Appendix C. Study Activities

Activity	Screening -30 to -1	Week 0/ Baseline	Week 4	Week 8	Week 12	Week 16	Week 20	Week 24/ET a	Week 31 Follow-Up Call b
Day	-30 to -1	Day 1	Day 29	Day 57	Day 85	Day 113	Day 141	Day 169	Day 218
Informed Consent	X								
Medical/Surgical History	X	X c							
Alcohol and Nicotine Use	X	X							
Pregnancy Tests d u = urine, s = serum	X(s)	X(u)	X(u)	X(u)	X(u)	X(u)	X(u)	X(u)	X(u)
Physical Exam c = complete, t = targeted	X(c)	X(c)	X(t)	X(t)	X(t)	X(c)	X(t)	X(c)	X(c)
Vital Signs e	X	X	X	X	X	X	X	X	X
Safety Laboratory Testing f c = complete, t = targeted	X(c)	X(c)	X(t)	X(c)	X(t)	X(c)	X(t)	X(c)	X(c)
Urinalysis	X	X	X	X	X	X	X	X	X
CASPAR Assessment	X								
FSH g	X								
PASI/% BSA Involvement	X	X	X	X	X	X	X	X	X
Assess Concomitant Medications	X	X	X	X	X	X	X	X	X
12 Lead ECG	X								
Infection Screening h	X								
Dispense Subject Diary i		X	X	X	X	X	X	X	X

Activity	Screening -30 to -1	Week 0/ Baseline	Week 4	Week 8	Week 12	Week 16	Week 20	Week 24/ET a	Week 31 Follow-Up Call b
Day	-30 to -1	Day 1	Day 29	Day 57	Day 85	Day 113	Day 141	Day 169	Day 218
DLQ j	X	X			X			X	
Randomization		X							
Risankizumab Administration k	X	X			X				
FUMADERM ® Dispensation l	X	X	X	X	X	X	X	X	
Blood Sampling for PK m		X	X			X	X	X	
Blood Sampling for ADA Assay m		X	X			X	X	X	
Subject Diary Review	X	X	X	X	X	X	X	X	
Monitor Adverse Events	X	X	X	X	X	X	X	X	
PPASI/PSI/NAPPA-CLIN j	X				X			X	
SPGA	X	X	X	X	X	X	X	X	
PSS j	X				X			X	
Monitor Compliance j	X	X	X	X	X	X	X	X	
Short Form SF-36 j	X				X			X	
Patient Benefit Index (PBI) j	X				X			X	
HADS j	X				X			X	
PtGA j	X				X			X	
EQ-5D-5L j	X				X			X	

a. Subjects that discontinue the study prior to the end of the study will have an Early Termination visit within 2 weeks after the decision to discontinue.

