### **Definition of Final Observation (Applicable to Safety Analyses)**

Final observation is defined as the last non-missing observation collected within 15 weeks (105 days) following the last dose of risankizumab or 1 week (7 days) after the last dose of FUMADERM® provided as study medication. In a sensitivity analysis, adverse events with an onset date until 7 weeks (49 days) after the last dose of FUMADERM® provided as study medication or until rollover into the extension study will be included.

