### **Definition of Analysis Windows**

All time points and corresponding time windows are defined based on Rx Days.

Analysis windows are constructed using the following algorithm:

- Determine the nominal Rx day for each visit (e.g., Week 4 [4 weeks after Baseline visit] equals Rx Day 29).

- In order to include all post baseline data, the first post-baseline interval starts on the first day after the first dose of study drug (Rx Day 2).
- Determine the window around a specific nominal Rx day by adding or subtracting half of the interval between adjacent visits (e.g., days between Week 4 and Week 8 is 28). The threshold between adjacent visits is determined by splitting the interval evenly between the visits. If the resulting split is between Rx days, then the threshold is determined as the midpoint between the adjacent visits. If the resulting split is on an Rx day, then the threshold is determined as being between that Rx day and the Rx day prior to it (e.g., the split between Week 4 and Week 8 would be between Rx Days 43 and 44).
- If more than one assessment is included in a time window the assessment closest to the nominal day will be used. If there are two observations equidistant to the nominal day, the later one will be used in analyses. If more than one assessment is included on the same day, then the worst assessment on that day will be used in analyses, except those specified in Section 11.0.

For subjects who were randomized and not dosed, the date of randomization will be used for determining window definitions.

The following analysis windows have been specified:

**Table 1. Visit Windows for Analysis of Vital Signs, PASI, BSA Involvement, sPGA, Urinalysis, Targeted Safety Laboratory Testing (ITT/Safety Populations)**

Window Label	Target Day	Interval
Baseline	1	≤ 1
Week 4	29	[2, 43]
Week 8	57	[44, 71]
Week 12	85	[72, 99]
Week 16	113	[100, 127]
Week 20	141	[128, 155]
Week 24	169	[156, 183 a ]

Rx Day calculated relative to first dose date of study drug. For subjects randomized but not dosed, Rx Day calculated relative to Randomization.

Targeted Safety Laboratory Testing includes CBC with differential count (hematology), ALT, AST, gamma-GT, alkaline phosphatase (AP) and serum creatinine.

a. For safety analyses (urinalysis and targeted laboratory testing): The minimum of upper bound and 105 or 7 days after the last dose for risankizumab and FUMADERM®, respectively.

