**Table 3. Visit Windows for Analysis of Complete Safety Laboratory Testing (Safety Population)**

Window Label	Target Day	Interval
Baseline	1	$\leq 1$
Week 8	57	[2, 85]
Week 16	113	[86, 141]
Week 24	169	[142, 197 a ]

Rx Day calculated relative to first dose date of study drug. For subjects randomized but not dosed, Rx Day calculated relative to Randomization.

Complete Safety Laboratory Testing includes all laboratory parameters (see [Table 8](#)) excluding CBC with differential count (hematology), ALT, AST, gamma-GT, alkaline phosphatase (AP) and serum creatinine.

a. For safety analyses: The minimum of upper bound and 105 or 7 days after the last dose for risankizumab and FUMADERM®, respectively.

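### The 7-day FUMADERM laboratory limit in SAP 11.3 can leave a compliant early-termination panel unanalysed, and no laboratory sensitivity analysis picks it up

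*SAP*

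**What the plan says.** **Laboratory limit.** SAP 11.3 (Analysis of Laboratory Data) says that "values observed more than 105 days after the last dose of risankizumab and 7 days after the last dose of FUMADERM will be excluded". The final-observation definition in SAP 6.0 uses the same limits: the last value "collected within 15 weeks (105 days) following the last dose of risankizumab or 1 week (7 days) after the last dose of FUMADERM".

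**ET visit.** Protocol 5.4.1 says that the ET procedures "must be completed within 2 weeks after the decision to discontinue", and footnote a of Protocol Appendix C says that these subjects "will have an Early Termination visit within 2 weeks after the decision to discontinue". The clock starts at the decision, not at the last dose. Appendix C makes the Week 24/ET panel a complete one.

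**Panels.** Under Protocol 5.3.1.1 (Clinical Laboratory Tests), the complete panel is drawn at Screening and Weeks 0, 8, 16 and 24. The targeted panel at Weeks 4, 12 and 20 has blood count with differential, ALT, AST, gamma-GT, alkaline phosphatase and creatinine, but no bilirubin.

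**Sensitivity analysis.** SAP 11.2.1, like Protocol 8.1.5, adds a longer FUMADERM period for adverse events: "In a sensitivity analysis, adverse events with an onset date until 7 weeks (49 days) after the last dose of FUMADERM". Neither document plans a laboratory counterpart. The Treatment Period text in Protocol 5.1 has safety data collected "up to 15 weeks after the last dose of risankizumab and/or 7 weeks after the last dose of FUMADERM".

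**Windows.** Footnote a of SAP Table 1 reads "For safety analyses (urinalysis and targeted laboratory testing): The minimum of upper bound and 105 or 7 days after the last dose", and footnote a of SAP Table 3 reads "For safety analyses: The minimum of upper bound and 105 or 7 days after the last dose". In both tables the marker stands only on the upper bound of the Week 24 row.

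**The concern.** The two clocks do not match. The ET visit may fall up to 14 days after the decision, while the FUMADERM laboratory limit is 7 days after the last dose. A site can follow the protocol exactly and the panel it draws still drops out of every laboratory table. The risankizumab limit is long enough that this does not happen on nominal dosing days. The sponsor addressed the unequal follow-up for adverse events through the 49-day analysis, but not for laboratory data.

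Bilirubin is the most exposed parameter. A FUMADERM subject who stops before the Week 8 draw has only the ET panel as a scheduled post-baseline value. If that panel is excluded, the subject cannot appear in the Hy's Law listing or on the bilirubin/ALT plot (SAP 11.3.2, Liver Function Tests) on the strength of scheduled samples. The loss falls only on subjects who stop early, whose safety data one would most want to see.

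**Working it through.** **1. The plan's own day counts.** In Protocol Appendix C, Week 16 is Day 113, Week 24 is Day 169 and the follow-up call is Day 218.
- 218 − 113 = 105, the risankizumab limit.
- 218 − 169 = 49, the FUMADERM adverse-event sensitivity limit.
- The Week 24 upper bounds also reproduce: 169 + 14 = 183 (Table 1) and 169 + 28 = 197 (Table 3).

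**2. When a FUMADERM ET panel is lost.** Let t be the day of the ET visit after the decision (0 to 14 if compliant) and g the days from last dose to decision. The panel is excluded if t + g > 7.

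| g | excluded t | share of the 15 possible days |
|---|---|---|
| −7 | none | 0/15 |
| 0 | 8 to 14 | 7/15 |
| 3 | 5 to 14 | 10/15 |
| 8 or more | all | 15/15 |

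**3. Risankizumab, nominal days.** Injections are on Days 1, 29 and 113. Assume the decision comes no later than the next scheduled injection, or Week 24. The longest gaps from last injection to a compliant ET are:
- 28 + 14 = 42
- 84 + 14 = 98
- 56 + 14 = 70

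All are within 105. Only with the two visits at opposite ends of the ±4-day window does the largest become 84 + 8 + 14 = 106.

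**4. Bilirubin example.** Last dose Day 30, ET Day 42. The gap is 12 days, which exceeds 7, so the panel is excluded. The Week 4 panel had no bilirubin and the Week 8 draw (Day 57) is never reached. No scheduled post-baseline bilirubin remains.

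**5. Illustrative size.** The documents give no stopping times or ET dates for this trial. The Protocol Introduction cites 24% discontinuation for adverse events on FUMADERM in another study: 0.24 × 55 = 13.2.
- Equal weight on days 0 to 14, g = 0: 13.2 × 7/15 = 6.2 panels.
- Earlier visits more likely, weights (15 − t)/120, g = 0: the weights for days 8 to 14 sum to 28/120 = 23.3%, and 13.2 × 0.233 = 3.1 panels.
- Varying g as in the table: from 0 to all 13.

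**6. Where the footnote is silent.** Rows carrying footnote a begin at Day 142 (Table 3) and Day 156 (Table 1). Take last doses on Days 1 to 168 with ET 0 to 14 days later, decision on the last-dose day. That gives 168 × 15 = 2520 combinations, of which 168 × 7 = 1176 are excluded by 11.3. Of those, 1008 (Table 1) and 910 (Table 3) fall in rows without the footnote. For ET on Day 142 or later, Table 3 with its footnote agrees with 11.3 in all 510 combinations.

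**The case against.** Several objections stand and limit the point.

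- **The 7-day rule follows the protocol.** It matches the on-treatment convention in Protocol 8.1.5, which confines the 49-day analysis to adverse events. No commitment is missed; a laboratory version is an addition.
- **Much of the signal is kept.** The targeted panel covers the laboratory parameters in the FUMADERM stopping criteria (Protocol 5.4.1.1). An on-treatment value that triggered discontinuation stays in the analysis. A Week 4 ALT or AST of at least 3 × ULN reaches the liver listing without bilirubin. Unscheduled repeats within 7 days, the Hepatic Adverse Event eCRF (Protocol 6.1.1.3) and the hepatic events in SAP Table 6 recover more.
- **Little is planned after ET.** The described contact is a telephone call, so a 49-day limit would add mainly the ET panels and repeats prompted by abnormal results, a selected sample.
- **ET visits are probably early.** The protocol prefers them before new therapy starts, which makes equal weighting of days 0 to 14 doubtful.

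A reader might infer two stronger things. The first is that Tables 1 and 3 contradict 11.3. They do not: 11.3 is an explicit exclusion for all laboratory assessments and can be applied before values are assigned to windows, and footnote a repeats the same cap. The counts in step 6 show where a footnote is absent, not where instructions clash. The second is that the exclusion flatters risankizumab. On counts of subjects crossing a threshold it cannot, because dropping FUMADERM values can only leave the FUMADERM count the same or lower it. For percentages, milder shift categories, final values and changes from baseline, the direction is not fixed.

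**Conclusion.** The point holds as a gap in completeness, of minor severity. A compliant FUMADERM ET panel drawn on days 8 to 14 after the last dose is not analysed, nor is any compliant ET panel if tablets stopped more than 7 days before the decision. On nominal dosing days no compliant risankizumab ET panel is lost. The bilirubin gap needs three things together: a stop before the Week 8 draw, an ET visit more than 7 days after the last dose, and no unscheduled sample inside the limit.

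The number affected cannot be determined from the documents and is likely small. The figures of about 3 or 6 of 13 panels rest on a discontinuation rate from another trial and on assumed ET timing. Completers lose nothing, because their last tablet is taken on the day of the Week 24 visit. The footnotes to Tables 1 and 3 are ambiguous: a programmer working from the tables alone could keep a late ET value in an earlier window.

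**What to change.** Keep the 7-day rule as the primary laboratory analysis.

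1. Add to SAP 11.3 one laboratory sensitivity analysis that retains all ET laboratory values, or that uses the 49-day FUMADERM limit already set for adverse events. With a compliant ET visit, the 49-day limit keeps the panel when the decision came up to 49 − 14 = 35 days after the last dose. Apply it to the potentially clinically important and CTCAE counts, the shifts to minimum and maximum, and the Hy's Law listing and plot.
2. State, in 11.3 or in the footnotes to Tables 1 and 3, that in the primary analysis the 105/7-day cap applies to every post-baseline laboratory window.

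The cost is a few lines of SAP text and a second date limit in the laboratory programs. No new visits or data are needed. The downside is one extra set of laboratory tables, which will include some off-drug values and some selected repeat samples and should be labelled as such.
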